## 5. Study Size and Power

Assuming that the proportions of subjects who successfully achieve primary endpoint are 0.6 for placebo arm and 0.8 for IVIG arm, with additional assumptions of normality approximation of difference of two proportions, the maximum sample size needed is 208 to provide at least 80% power assuming a drop-out rate of 15%. That is, 176 subjects with complete data for primary endpoint (clinical status at baseline and Day 7) are needed to maintain at least 80% of statistical power under overall type I error of 0.05.

## 6. Analysis Populations

In the definitions below, an Analysis Population refers to a particular set of participants. Additional censoring rules for analyses based on these populations are described in relevant sections of the SAP. The definition applies to analyses for scheduled IDMC meetings and final analysis.

- Screened Population – The Screened Population includes all subjects who are screened.
- Enrolled Population – The Enrolled Population includes all subjects who enrolled in the study.
- Intent-to-Treat (ITT) Population – The Intent-to-Treat Population includes all subjects who are randomized.; Analysis will be conducted according to the study arm in which subjects are randomized, regardless of randomization errors or protocol violations.
- Safety (SAF) Population – The Safety Population includes all subjects who are randomized and received any amount of IVIG or placebo. The analysis will be conducted according to the treatment which subjects actually received. This analysis population is a subset of the ITT population.
- Per-Protocol (PP) Population - The Per-Protocol Population includes subjects who receive at least 75% of the planned dose (3 completed infusions of IVIG or placebo) without major protocol deviations that would potentially interfere with the efficacy assessment. This will be determined in consultation with the Octapharma Study leadership during blinded data review. The criteria for exclusion of subjects from the PP Population will be determined and documented prior to scheduled unblinding. The analysis will be conducted according to the treatment which subjects actually received. This analysis population is a subset of the ITT population.

## Summary of Planned Analysis, by Population

Analysis	Screened	EP	ITT	Safety	PP
Disposition	√				
Subject Assessment		√			
Study Treatment Dosage			√	√	√
Primary Efficacy			√		√
Secondary Endpoints			√		√
Exploratory Endpoints			√		
Safety				√	
Additional Efficacy			√	√	√
Additional Safety				√	
Concomitant Medications and Procedures				√	

### 7. Blinded Data Review

Prior to scheduled study unblinding, the data will be reviewed in a blinded fashion for final data analysis decisions. Based on analysis needs, the lead statistician will develop specific listings for this review and will document decisions made prior to unblinding. These decisions may include (but not necessarily be restricted to) protocol violations leading to inclusion/exclusion of subjects in the different analysis populations and/or data points in specific analyses. More specifically, protocol violations will include those documented in the protocol violation CRF as well as violations that can be detected directly from the data base. Decisions on missing data, identification of prohibited medications and final imputation of endpoints will be done during this blinded review phase. Blinded data review may also include clinical evaluation of safety data for reasonableness or to issue clinical queries to the site if needed. Any decisions affecting the analysis will be described in internal documentation and the clinical study report.

### 8. Independent Data Monitoring Committee (IDMC) Meeting Scope and Time Point

Due to accelerated enrollment, there have been two scheduled IDMC meetings to review interim data (i.e., not including operational meetings) for safety monitoring purposes. The time points specified below were the timepoints for the scheduled IDMC meetings, and the corresponding analysis scope is specified.

1. Approximately 44 subjects (first 25% of data collected) for safety review

The analysis scope of this IDMC review focuses on safety data review. The blinded study statistician prepared overall data presentations for the study team, whereas the dedicated unblinded statistician prepared parallel data presentations by treatment assignments and provided unblinded data to the IDMC only.

Proportions of subjects screened, enrolled, randomized, and length of follow-up were provided by site for the Screened Population. Screening failure reasons were summarized. Furthermore, subject disposition based on the Full Analysis Population, including subject status. Dose administration status overall and by treatment arm was provided for the Safety Population.

Baseline information, demographics, treatment status, primary reason for early termination, and baseline laboratory values were tabulated and summarized for the Safety Population. In addition, adverse events (AEs), serious adverse events (SAEs), treatment-emergent adverse events (TEAEs), and TEAEs related to study drug by maximum severity was summarized by System Organ Class (SOC) and Preferred Term (PT) by CTCAE grades.

Demographic information, screening failure reasons, protocol deviations, subject treatment status, reasons for early termination, and adverse events were listed.

2. An additional data review at 50% of subjects enrolled, based on similar reports to those specified above, without a formal meeting.

Further details with respect to IDMC decision reviews and decision making can be found in the IDMC Charter and meeting minutes. An additional meeting is planned after 100% of data is accumulated.

## **9. Subject Disposition**

The frequency and percentage of subjects screened, enrolled, randomized, as well as screening failure reasons will be tabulated based on the Screened Population. The number of subjects enrolled and randomized at each site will be tabulated by treatment arm using the ITT Population.

Final status, including frequency and percentage of subjects who completed the study, were lost to follow-up, or terminated early along with primary reasons for discontinuation will be tabulated by treatment arm for the ITT Population.

The frequency of protocol deviations will be summarized by treatment arm for the ITT Population. Furthermore, all protocol deviations classified as major and/or significant with respect to the evaluation of the primary endpoints will be listed separately.

## 10. Summary of Subject Assessment

The following assessments will be summarized:

- Demographics and Baseline Characteristics (ITT population, Safety Population, and Per Protocol Population)  
Baseline demographic and characteristics (e.g. age, gender, height, weight, race, ethnicity)
- Medical History (ITT population, Safety Population, and Per Protocol Population)  
Medical history data by Medical Dictionary for Regulatory Activities (MedDRA) System Organ Class and Preferred Terms.
- Physical Examinations, Vital Signs, Weight, Oxygen Saturation (SpO2), Laboratory Results (Safety Population)  
Physical exam, vital signs, weight, SpO2, spirometry and laboratory results including chemistry and hematology, will be summarized by visit.
- Clinical Status and Oxygen/Ventilator Status (ITT population and Safety Population)  
The clinical status and ventilator status will be tabulated according to the categories defined in the protocol by visit, regardless of prohibited medication use, based on shifts from baseline displays. Additional summaries may be provided, suppressing information following prohibited medication use, if use of prohibited medications is highly prevalent.
- rRT-PCR (ITT population)  
The result of rRT-PCR will be tabulated according to predefined categories by visit and sample type.
- Chest X-ray (Safety Population)  
The assessment of pulmonary infiltrate and pleural effusion over time will be tabulated separately for pre-specified age strata and visit.

- Borg Dyspnea Scale and McGill Quality of Life Single Item Scale (ITT Population)

The scale measures will be summarized by descriptive statistics by visit.

## **11. Analysis of Study Treatment Dosage**

Treatment dosage will be presented descriptively by study day and treatment, including but not limited to number of planned and actual doses and number of doses stopped or interrupted. All planned and actual doses will be listed as well.

The analysis will be presented for the ITT Population and repeated for the Safety and Per-Protocol Populations. Listings will be provided to support the descriptive analysis.

## **12. Definition of Study Outcome and Endpoint**

This section includes definition of metrics for analysis specified under the scope of this SAP. The handling of missing data, including data collected after prohibited medication use, is detailed in the corresponding analysis section for each metric.

### **Stabilized or Improved Clinical Status / Maintenance or Improvement on the Clinical Status**

A subject's clinical status is considered stable or improved if the clinical status category is the same or a better clinical category from baseline to the study day of interest.

### **Proportion of subjects with maintenance or improvement by at least one category on the 6-point clinical status scale**

This is defined as the proportion of subjects who were identified as stable (same clinical status as baseline) or improved (at least 1 level decrease in clinical status score from baseline) at the visit day.

### **Proportion of subjects with improvement by at least one category on the 6-point clinical status scale**

This is defined as the proportion of subjects who were identified as improved (at least 1 level decrease in clinical status score from baseline) at the specified visit day.

### **Time to recovery through Day 33 where recovery is defined as a clinical status of 1 or 2**

Time to recovery is defined as (first date of clinical status 1 or 2 – randomization date + 1). Subjects which do not have this event, or who are considered failures based on clinical status imputation methods corresponding to the primary analysis, will be considered censored at Day 33.

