6.1.4 Follow-up Visits 6 and 7 (Day 14 and Day 21)

The following safety assessments will be performed at Day 14 and Day 21 (see Section 6.1.6. if subject has been discharged):

1. Vital signs
2. SpO₂ saturation (see Section 7.2.4)
3. Clinical Status and Oxygenation/Ventilator Status Evaluation
4. Modified Borg Dyspnea Scale
5. MQoL-SIS
6. AE monitoring
7. Concomitant medication use

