6.1.6 Telephone Visits

If a subject is discharged from the hospital at any time during the course of their participation in the study, a pulse oximeter will be provided to them to monitor their oxygen saturation at home. The Research Coordinator or other qualified research team member will contact the subject on Day 7 (if discharge took place on Day 5 or earlier), Day 14, Day 21, and Day 33 (if discharge took place prior to Day 33) at approximately the same time (± 2 hours) as the pre-infusion SpO₂ measurement recorded at Baseline (Day 1), to collect the following data points:

1. Clinical Status
2. SpO₂ saturation taken on resting room-air
3. AE and Concomitant medication review
4. Modified Borg Dyspnea Scale
5. MQoL-SIS

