7.2 Efficacy Assessments

7.2.1 Clinical Status

Clinical status categories will be defined according to the following 6-category clinical status scale:

1. Hospital discharge or meet discharge criteria (discharge criteria are defined as clinical recovery, ie, no fever, respiratory rate, oxygen saturation return to normal, and cough relief).
2. Hospitalization, not requiring supplemental oxygen.
3. Hospitalization, requiring supplemental oxygen (but not NIV/HFNC), as defined by A-a Gradient < 150 mmHg.

4. ICU/hospitalization, requiring NIV/HFNC therapy, as defined by A-a Gradient ≥ 150 mmHg.
5. ICU, requiring ECMO and/or IMV.
6. Death.

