7.2.2 Oxygenation/Ventilator Status

Oxygenation status and/or ventilation status will be recorded at each scheduled visit, and in between visits if there is a change in status. The following will be captured:

Supportive measure required to maintain oxygen saturation:

- Nasal canula ≤ 4 L/min
- Nasal canula > 4 L/min
- Face mask
- Non-breather face mask
- Non-invasive ventilation
- Invasive mechanical ventilation.

Data will be used to calculate the incidence of invasive mechanical ventilation, duration of invasive mechanical ventilation and other changes in oxygenation status as required.

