#### **4.6 Reporting Timeframe of Measurement for Analysis**

For analyses of primary and secondary efficacy endpoints, including clinical status and RT-PCR, the latest observation within any given study day will be used. If the observations for the Day 7 visit falls outside of the 24-hour window of the study day or the Day 14 visit falls outside of the 48-hour window of the study day, the observation will be considered as missing and the imputation described in Section 4.1 will apply as appropriate. Otherwise, unless specifically stated otherwise, analyses will be conducted based on nominal visits.

For summary analyses of efficacy assessment, including oxygenation, oxygen saturation, modified Borg Dyspnea Scale and McGill Quality of Life Single-Item Scale (MQoL-SIS) and safety parameters (including vital signs, clinical laboratory evaluations and chest CT/chest X-ray findings), the latest observation within the study day during treatment period will be used. No imputation will be made for these assessments.

For safety analysis with adverse events, the observation with highest severity within the study day during treatment period will be used. No imputation will be made.

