#### **Time to first improvement through Day 33 where recovery is defined as a clinical status of 1 or 2**

Time to recovery is defined as (first date of clinical status improvement [defined as a 1-point or more decrease in scale from baseline] – randomization date + 1). Subjects which do not have this event, or who are considered failures based on clinical status imputation methods corresponding to the primary analysis, will be considered censored at Day 33.

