#### **Length of hospital stay (time to discharge) through Day 33**

Length of hospitalization is defined as (date of discharge [event] – randomization date + 1). Subjects which do not have this event will be considered censored at Day 33. Only the index hospitalization will contribute to this endpoint; readmittance will not be considered for analysis, but these incidences will be provided in data listing. Additional event (hospital discharge) and censoring (no hospital discharge) details are included in a subsequent section.

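### SAP section 12 does not state the source of the recovery and first-improvement dates; on its nominal-visit default, recovery can be dated days after the subject left hospital

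*SAP*

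**What the plan says.** SAP section 12 computes time to recovery as the "first date of clinical status 1 or 2" minus the randomization date plus 1. Time to first improvement uses the "first date of clinical status improvement", meaning a drop of one point or more from baseline. Neither definition names the source of the date. SAP section 14 analyses both descriptively, following the Kaplan-Meier analysis of length of stay.

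Four other provisions bear on that date:

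- **Schedule.** Protocol 6.1.2 to 6.1.5 list clinical status on Days 1–4, 7, 14, 21 and 33. For inpatients after Day 7, "The following safety assessments will be performed at Day 14 and Day 21", and then at Day 33. Protocol 6.1.6 has discharged subjects telephoned on "Day 7 (if discharge took place on Day 5 or earlier), Day 14, Day 21, and Day 33", and clinical status is among the items collected.
- **Default timing.** SAP 4.6, after its rules for the Day 7 and Day 14 windows, says: "Otherwise, unless specifically stated otherwise, analyses will be conducted based on nominal visits".
- **Meaning of category 1.** Protocol 7.2.1 defines it as "Hospital discharge or meet discharge criteria".
- **Dates already held.** The length-of-stay definition in SAP section 12 starts "Length of hospitalization is defined as (date of discharge [event", so the discharge date is collected and used. Protocol 7.2.2 adds: "Oxygenation status and/or ventilation status will be recorded at each scheduled visit, and in between visits if there is a change in status".

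**The concern.** Discharge is recovery on this scale, yet the plan never links the two dates. After Day 7 a clinical status score arises only at widely spaced visits. A subject who goes home between visits is next scored by telephone. If that contact supplies the event date, the trial reports the subject as discharged first and recovered later.

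The SAP does bring outside information into clinical status, but in one direction only. Section 4.1 sets status 6, 5 or 4 from death, ECMO or IMV, and ICU data when an assessment is missing. No rule sets status 1 from discharge.

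For a descriptive endpoint the Kaplan-Meier estimates are the result. Late event dates move the medians, and two programmers could obtain medians several days apart from the same definition.

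**Working it through.** The documents give no event rate or target median for these endpoints, so there is no planned figure to reproduce.

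**1. Visit gaps.** Nominal days after Day 7 are 14, 21 and 33; Protocol Table 2 tolerances are ±1 day (Visit 5), ±2 days (Visits 6 and 7) and ±3 days (End of Study).

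| Interval | Nominal gap | Shortest | Longest |
|---|---|---|---|
| Day 7 to 14 | 7 | 12 − 8 = 4 | 16 − 6 = 10 |
| Day 14 to 21 | 7 | 19 − 16 = 3 | 23 − 12 = 11 |
| Day 21 to 33 | 12 | 30 − 23 = 7 | 36 − 19 = 17 |

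**2. One subject.** Randomization is on Day 1 (Protocol 6.1.2), so the elapsed time equals the study day. Day 9 is the first discharge day outside the Visit 5 window (Days 6–8).

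- Time to discharge: 9 − 1 + 1 = 9.
- Time to recovery, nominal Visit 6: 14 − 1 + 1 = 14, which is 5 days after going home.
- Time to recovery, actual Visit 6 date within Days 12–16: 12 to 16, which is 3 to 7 days after going home.

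**3. Mean delay on nominal days.** Delay = next visit day − event day, with event days uniform within each interval.

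- Days 8–14: (6+5+4+3+2+1+0)/7 = 21/7 = 3.0.
- Days 15–21: the same, 3.0.
- Days 22–33: (11+10+…+0)/12 = 66/12 = 5.5, with a maximum of 11.

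With exponential recovery times (assumed medians of 6 to 25 days), the mean delay for events after Day 7 is about 4 days.

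**4. Medians and power.** Illustrative model, all assumed: log-normal recovery times, SD of log 0.8, 104 per arm, events moved to the next visit. The ranges are over repeat runs and mostly reflect how the sample median is defined.

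| True medians | Arms tied, nominal days | Log-rank power, exact / visit-dated |
|---|---|---|
| 14 vs 10 | 47–55% | 0.79 / 0.81 |
| 13 vs 9 | 74–80% | 0.85 / 0.86 |
| 12 vs 8.5 | 89–93% | 0.82 / 0.84 |

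Ties depend on where the medians lie. On nominal days, 16 vs 12 ties in only 12% of trials and 9 vs 6 in 5%.

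With actual visit dates spread over the Table 2 windows, ties fall to about 3–6% in the three tabulated scenarios. The medians are still late: for 13 vs 9, exact-date medians of about 13.4 and 9.5 become about 16.4 and 13.6. The difference shrinks from about 4 days to about 3 (16.4 − 13.6 = 2.8).

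The distortion can also go the other way. With exponential times on nominal days, true medians 4 days apart (assumed 24 vs 20) show as 12 days apart.

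**The case against.** A reader might infer that the SAP prescribes visit dating, so that the medians must fall on visit days and the arms will often tie. The documents do not support that. The definitions subtract calendar dates and say date, whereas neighbouring definitions in SAP section 12 say visit day when they mean it. The nominal-visit default yields where something else is stated, and a formula in dates arguably states it. Because category 1 is discharge and that date is held, a programmer could date recovery at discharge without breaking any rule. Ties on visit days arise mainly under nominal-day coding and for medians between Days 7 and 14.

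Two limits on the schedule argument also stand. Protocol 6.1.3 and Table 2 allow Visit 5 on the discharge day in some cases and as late as Day 8, so a Day 8 discharge can be scored correctly. The footnote attached to the clinical status row of Table 1 was not available to this review, so recording between visits cannot be ruled out completely.

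Finally, the impact is modest: both endpoints are descriptive and outside the hierarchy, log-rank power is almost unchanged, and time to discharge, which leads the key secondary endpoints, uses exact dates.

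These arguments defeat the claim that the plan mandates late dates. They do not supply the missing rule, and an open date source combined with a nominal-visit default still favours the late reading.

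**Conclusion.** The point holds as a gap in the definition with a foreseeable consequence. SAP section 12 leaves the event date's source open, and read with section 4.6 and the visit schedule it can place recovery days after discharge.

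The size is a mean delay of 3.0 days for events on Days 8–21 and 5.5 days for Days 22–33, given nominal days and uniform event times. Medians about 3 to 4 days late under actual visit dates, and the altered differences between arms, rest on assumed recovery distributions and show direction and order of size only. No confirmatory test is affected. It is worth correcting because the estimates are all these two endpoints report, and the correction is nearly free.

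**What to change.** In SAP section 12, define the event date for both endpoints as the earlier of:

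- (a) the date of the first qualifying clinical status assessment, using its actual date; and
- (b) the index hospital discharge date, taken as status 1.

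Apply to (b) the rule that SAP 4.1 sets for length of stay: a discharge on or after the start of prohibited medication is not an event.

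Do not add between-visit changes in oxygen support from Protocol 7.2.2 unless the eCRF records a change that maps unambiguously to a scale category. The support list there has no room-air or high-flow entry, and steps such as a lower cannula flow need not change the category. Categories 3 and 4 are also tied to the A-a gradient, which Protocol 7.2.4 records only at baseline and Day 7.

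The cost is one SAP sentence and minor programming, with no new data. Improvements short of discharge would remain visit-dated, and the report should say so.

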##### **4.1 Missing Data**

The latest patient status available prior to Day 7 will be used to determine clinical status in the absence of a clinical status assessment. If a death date is prior to Day 7, clinical status at Day 7 will be identified as a 6. Otherwise, if a subject's last status reflects that they were in the ICU and receiving ECMO and/or IMV, clinical status will be imputed as a 5. Otherwise, if a subject's last status reflects that they were in the ICU and not receiving ECMO and/or IMV, clinical status will be imputed as a 4. If the LOCF clinical status value for a patient is higher than these imputed values or if a subject status cannot be derived based on available information on ECMO, IMV, or ICU status, the last observation carried forward (LOCF)

will be used to impute patient values. Subjects with no post-baseline clinical status assessment, or prohibited medication use, on or prior to Day 7 will be imputed as failure.

An imputation analogous to the primary endpoint will be performed for the secondary endpoint of clinical status at Day 14.

For the secondary endpoint length of hospitalization, Subjects who are still hospitalized as of Day 33, subjects with missing end dates due to withdrawal, subjects with unusable end dates due to prohibited medication use, or those who died on/prior to Day 33 will be censored at Day 33. Discharge occurring on or after the start date of prohibited medication use will not be considered an event.

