## **13. Analysis of Primary Efficacy Endpoint**

The primary analysis will be based on the ITT Population. The null hypothesis of no difference in proportion of subjects who reach success (clinical status not worse than the clinical status category at Baseline at Day 7) in two treatment groups will be tested versus the alternative hypothesis that there is a difference between proportions of subjects who reach success in two groups. Hypothesis testing will be performed using Cochran-Mantel-Haenszel (CMH) stratified by age category ( $\leq 65$  versus  $> 65$ ) at a two-sided 0.05 significance level. The difference in proportions between two groups with standard deviation, and 95% Miettinen-Nurminen (1985) confidence interval (CI) will also be provided.

If the CMH fails the Mantel-Fleiss criteria (1980), a chi-squared test will be the basis of evaluation and unweighted asymptotic CIs for the difference in proportions will be used. If, when implementing a chi-squared test, an expected cell count  $< 5$ , Fisher's exact test will be used and exact (Santner-Snell, 1980) CIs will be provided.

For subjects with clinical status assessment at Baseline (Day 1), missing data at Day 7 will be imputed based on the method described in Section 4.1. Subjects with missing data at Baseline (Day 1) will be imputed as failure.

Subjects who use prohibited medication (medications being administered as part of other experimental studies or the use of experimental non-IVIG products, COVID-19 convalescent plasma, or interferons) on or before Day 7 will be counted as failure. Prohibited medications will be identified during blinded review described in Section 7.

Shifts from Baseline (Day 1) at Day 7 in terms of the 6-point clinical status scale will be reported (descriptive analysis).

The durability of the treatment effect will be reviewed based on the comparison of proportions who are stabilized or improved between treatment arms at Day 14, Day 21, and Day 33 in the final analysis. No formal hypothesis testing will be conducted for the Day 21 and Day 33 analyses and the descriptive comparison will be carried out based on the method applied for the primary analysis. Graphical representations of clinical status, and changes from baseline, over time will be presented by treatment group.

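### Time to recovery and time to first improvement: the SAP censors at Day 33 every subject who fails under the Day 7 imputation rule, whatever the event date, and so discards observed events

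*SAP*

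**What the plan says.** SAP Section 12 defines the first endpoint by the date of the first good status: "Time to recovery is defined as (first date of clinical status 1 or 2 – randomization date + 1". Time to first improvement is built the same way, from the first date with a drop of at least one point from baseline. Neither event definition mentions prohibited medication. Both entries then censor subjects who lack the event, "or who are considered failures based on clinical status imputation methods corresponding to the primary analysis, will be considered censored at Day 33".

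The failures of the primary analysis are set out in two places.

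- SAP Section 4.1: "Subjects with no post-baseline clinical status assessment, or prohibited medication use, on or prior to Day 7 will be imputed as failure".
- SAP Section 13: "Subjects with missing data at Baseline (Day 1) will be imputed as failure", and prohibited medication "on or before Day 7 will be counted as failure".

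For length of stay, Section 4.1 works by date: "Discharge occurring on or after the start date of prohibited medication use will not be considered an event".

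On data after prohibited medication, the opening of Section 12 says: "The handling of missing data, including data collected after prohibited medication use, is detailed in the corresponding analysis section for each metric". The relevant analysis section, Section 14, says only that the two endpoints are analysed descriptively, on the model of the Kaplan-Meier analysis of hospital stay. The protocol gives no censoring rule for either endpoint.

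**The concern.** A rule made for a yes/no outcome at Day 7 is applied to a time-to-event outcome that runs to Day 33. It flags the subject, not the event. A subject with a dated, observed recovery can therefore enter the Kaplan-Meier curve as not recovered through Day 33, because of something that happened after the recovery or because early assessments are missing.

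The curves and medians for the two endpoints are at stake. If missing early data or use of prohibited products differs by arm, the distortion differs by arm too. There is also a question of consistency. Status 1 includes hospital discharge, so one discharge can be scored differently for recovery and for length of stay. Two programmers could produce different curves and both claim to follow the SAP.

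**Working it through.** The plan gives no figure for this point, so the check is mainly one of rule logic.

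**Step 1: what the clause adds.** The first part of the censoring sentence covers every subject without the event. The second part can change the result only for a subject who has an observed event. Its only effect is to turn a dated event into censoring at Day 33.

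**Step 2: who is flagged.** There are three explicit routes: no post-baseline assessment by Day 7, prohibited medication by Day 7, and missing baseline. A fourth is arguable: a Day 7 status imputed as worse than baseline. SAP Section 4.6 feeds that fourth route, because a Day 7 assessment outside its window is treated as missing and goes to imputation.

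**Step 3: literal Section 12 beside the length-of-stay date rule, for time to recovery.** Entries are (day, event), with 1 = event and 0 = censored.

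| Subject | Section 12, literal | Date rule |
|---|---|---|
| Recovery Day 4, medication Day 6 | (33, 0) | (4, 1) |
| No assessment by Day 7, recovery Day 14 | (33, 0) | (14, 1) |
| Missing baseline, recovery Day 5 | (33, 0) | (5, 1) |
| Medication Day 6, recovery Day 20 | (33, 0) | (33, 0) |
| Recovery Day 5, medication Day 20 | (5, 1) | (5, 1) |
| Medication Day 8, recovery Day 20 | (20, 1), if Section 12 stands alone | (33, 0) |

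The first three rows are observed recoveries that the stated rule discards. The third row applies to time to recovery only: without a baseline, improvement is undefined, so nothing is lost for time to first improvement. The last row depends on a reading that the SAP leaves open.

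**Step 4: illustration of size, prohibited-medication route only.** All rates here are assumptions. There are 208 subjects, and 70% recover by Day 33 with a constant hazard, so the share not recovered by the end of day k is S(k) = 0.3^(k/33). A share q starts prohibited medication on a day P that is uniform over Days 1 to 33 and independent of recovery.

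- Recoveries erased although dated before the medication: 208 × q × (1/33) × Σ over P = 1 to 7 of [1 − S(P−1)] = 208 × q × 0.0215.
- Recoveries on or after a medication start on Day 8 or later, which literal Section 12 does not exclude: 208 × q × (1/33) × Σ over P = 8 to 33 of [S(P−1) − 0.3] = 208 × q × 0.1651.

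| q | Erased | Not excluded | Recovered by Day 33, literal vs date rule |
|---|---|---|---|
| 2% | 0.1 | 0.7 | 69.7% vs 69.4% |
| 5% | 0.2 | 1.7 | 69.3% vs 68.5% |
| 10% | 0.4 | 3.4 | 68.5% vs 67.1% |
| 20% | 0.9 | 6.9 | 67.0% vs 64.2% |

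A simulation on the same assumptions agrees to within about 0.1 of a recovery and 0.1 of a percentage point. The missing-data routes are not in this table, because the documents give no rate from which to size them.

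**The case against.** **A composite-type choice is legitimate.** Carrying the primary failure rule into related clinical-status endpoints can be defended as a strategy. This stands for recoveries after early prohibited medication, which the date rule also excludes (fourth row of the first table). It does not justify discarding a recovery dated before the medication, or one observed after a gap in early assessments.

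**The rule may be meant to move with the visit.** The clause refers to methods corresponding to the primary analysis, and Section 4.1 extends the rule once: "An imputation analogous to the primary endpoint will be performed for the secondary endpoint of clinical status at Day 14". An analogous rule at later visits is therefore a possible reading. The SAP does not state it for these two endpoints, and a moving cut-off would still ignore the event date.

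**An imputed Day 7 status is not clearly a failure.** The SAP uses the words imputed as failure only for the three explicit routes. A subject whose Day 7 status is derived or carried forward may or may not be worse than baseline, and it is open whether the clause reaches that subject. This stands, so the fourth route is called arguable here. If the clause does reach it, a subject imputed at status 5 on Day 7 and seen at status 1 on Day 21 is censored, while a subject observed at status 5 on Day 7 with the same later record counts as recovered.

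**Rescued recoveries from Day 8.** A reader might infer that the SAP credits recoveries after prohibited medication started on Day 8 or later. The documents do not say so. Section 12 sends the matter to the analysis section, and Section 14 models both endpoints on the length-of-stay analysis, which censors end dates made unusable by prohibited medication. On that reading these recoveries would not count. The link is not explicit, so the right statement is that the SAP leaves the point open.

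**Little is hidden.** Sections 10 and 17 still summarise clinical status by visit, and Section 10 does so regardless of prohibited medication. This stands and limits the harm, but it does not correct the time-to-event curves.

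**Conclusion.** The concern holds for the censoring clause. As written, it discards observed recoveries and improvements in identifiable subjects and conflicts with the date rule that the same SAP uses for length of stay. For prohibited medication from Day 8 the SAP is unclear, not demonstrably wrong.

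The consequence is limited. Both endpoints are other secondary endpoints, analysed descriptively and outside the six-endpoint hierarchy, so the type I error and the confirmatory conclusions are untouched.

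The number of affected subjects cannot be derived from the documents and is probably small. On the assumed rates above, the prohibited-medication route erases fewer than one recovery among 208 subjects even at 20% use. A reader might reach 3 to 8 lost recoveries per arm by supposing that 5% to 15% of 104 are imputed failures and that half of them recover (104 × 0.05 × 0.5 = 2.6; 104 × 0.15 × 0.5 = 7.8). The documents support neither rate. The 15% in the sample-size section is drop-out, and drop-outs with some post-baseline data receive a derived or carried-forward status, not automatic failure. That count would also include recoveries after prohibited medication, which a date rule excludes as well.

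The correction is still worth making, because the rule gives wrong event times and costs almost nothing to repair.

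**What to change.** In the Section 12 entries for time to recovery and time to first improvement, replace the imputed-failure clause with:

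*An observed recovery (or improvement) counts as an event if it is dated before the start of any prohibited medication. Events on or after that date do not count, whatever day the medication starts. Subjects without a counted event, including those who die, are censored at Day 33.*

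For time to first improvement, add that subjects with missing baseline are censored at Day 33. State in Section 14 that this rule governs the Kaplan-Meier analyses of both endpoints, which closes the question for medication started on Day 8 or later. The entry for time to first improvement also still carries the recovery wording in its title and its definition, which can be corrected in the same edit.

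The cost is two SAP sentences and a cross-reference, with no new data and no change to trial conduct. The change should be made before unblinding.
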